2.5 Data Monitoring Committee and Other External Committees

2.5.1 Data Monitoring Committee

An independent DMC will review safety data to ensure safety of subjects in the trial. The full role of the DMC will be defined in a separate DMC charter. The DMC will review unblinded accumulating data on a regular basis and make recommendations to BMS and the Executive Committee regarding subjects currently enrolled and yet to be enrolled in the trial. The DMC may recommend suspension of enrolment or early termination of the trial for safety reasons. See [Section 7.11](#) for additional information.

The DMC will consider available endpoint information, in addition to safety events, before making any study stopping recommendations to the Executive Committee and Sponsor, as per guidelines set forth in the DMC charter.

2.5.2 Executive Committees

The executive committee will be a small body comprised of academic leaders. The executive committee will provide advice on overall design, study endpoints and recommendations for study sites, and will review results from interim and final analyses with Sponsor.

3 OBJECTIVES

3.1 Primary

The primary objective is to evaluate the effects of various doses of BMS-986231 compared to placebo on clinically relevant hypotension (defined by SBP < 90 mm Hg or symptoms of hypotension)

3.2 Secondary

Secondary objectives include the following:

- Assess the effect of BMS-986231 on NT-proBNP
- Assess the effect of BMS-986231 on patient-reported resting dyspnea as measured by the 11-point Numerical Rating Scale (NRS)

3.3 Safety

Safety objectives include the following:

- Evaluate the effect of BMS-986231 on the incidence of symptomatic hypotension
- Evaluate the effect of BMS-986231 on the incidence of SBP < 90 mm Hg

- Evaluate the incidence of dose reductions, temporary interruptions, and permanent discontinuation of BMS-98623 infusions
- Evaluate the safety and tolerability of a continuous 48-hour infusion of BMS-986231 in hospitalized HFrEF subjects with ADHF
- Evaluate the effect of BMS-986231 on high sensitivity (Hs) Troponin T
- Assess the effect of BMS-986231 on mortality at Day 182

[REDACTED]

4 ENDPOINTS

4.1 Efficacy Endpoints

4.1.1 *Primary Efficacy Endpoint*

There is no primary efficacy endpoint. The primary safety endpoint is discussed in [Section 4.2.1](#).

4.1.2 Secondary Efficacy Endpoints

Secondary endpoints include the following:

- Change in NT-proBNP from baseline to Hour 24, 48, 72, 120 or discharge (whichever comes first), and at Day 32
- Change in patient-reported resting dyspnea from baseline through Hour 72, as measured by the area under the curve (AUC) of the 11-point Numerical Rating Scale (NRS) obtained at baseline, and Hours 6, 12, 24, 48, and 72

4.2 Safety Endpoints

4.2.1 Primary Safety Endpoint

The primary safety endpoint is the incidence of clinically relevant hypotension, defined by SBP < 90 mm Hg (confirmed by a repeated value < 90 mm Hg, see [Section 8.1](#)) or symptoms of hypotension, up to 6 hours after the end of study drug infusion.

4.2.2 Other Safety Endpoints

Other safety endpoints include the following:

- The incidence of symptomatic hypotension up to 6 hours after the end of study drug infusion
- The incidence of SBP < 90 mm Hg (confirmed by a repeated value, see Section 8.1) up to 6 hours after the end of study drug infusion
- Change in Troponin T from baseline to Hour 24, 48, and 72
- Percentage of subjects who have died (all- cause and CV(cardiovascular) related) through Day 182

Additionally, the percentage of subjects with discontinuation due to symptomatic hypotension, as well as percentage of subjects with down-titrations, interruptions or discontinuations as a result of low blood pressure, either protocol specified clinically relevant hypotension, or asymptomatic decreases will be assessed. Other safety endpoints include the incidence of Adverse Events and Marked Laboratory Abnormalities, changes from baseline in vital signs, ECGs, physical measurements and laboratory assessments through Hour 120 or discharge, whichever comes first. The incidence of Serious Adverse Events will be assessed though Day 32.

[REDACTED]

maximally tolerated dose approximately 50-70%, based on detecting an increase of 3-fold or 2.5-fold in incidence, and using sample decision rules that are consistent with above. Also, the design will provide an option to select a titrated 12 µg/kg/min dose approximately 60% of the time when that dose is tolerated, but a non-titrated 12 µg/kg/min dose is not tolerated. Conversely, the study design will not identify a maximally tolerated dose is established from Part II (Cohort 2) approximately 80%-85% of the time when no maximally tolerated dose exists.

6 STUDY PERIODS, TREATMENT REGIMENS AND POPULATIONS FOR ANALYSES

6.1 Study Periods

Screening period starts from 18 hours prior to start of study drug infusion to Hour 0 (the start of study drug infusion). In-hospital follow-up starts from the end of study drug infusion to Hour 120 or discharge, whichever comes first. Day 32 follow-up occurs 32 days after the start of study drug infusion. Day 182 follow-up occurs 182 days after the start of study drug infusion.

Please see the study design ([Section 2.1](#)) for the details on study periods.

6.2 Treatment Regimens

BMS will provide Investigational drug product BMS-986231 for infusion (active pharmaceutical ingredient BMS-986231 formulated with Captisol®) to all sites. In addition, Potassium acetate is to be locally sourced by sites within the US and will supplied to all ex-US sites.

Subjects will be administered study medication as a continuous IV infusion over 48 hours.

Body weight measured at screening will be used for dose calculations.

See Pharmacy Manual for additional dosing information.

6.3 Populations for Analyses

The following populations will be used for the analyses:

- The Enrolled Subjects Data Set will consist of all subjects who sign informed consent
- The Randomized Subjects Data Set will consist of all randomized subjects who have started study drug infusion. This is also known as the Intent to Treat (ITT) population. Data in this data set will be analyzed based on randomized treatment group
- The Treated Subjects Data Set will consist of all subjects who receive any study drug infusion. This will be the primary safety data set. Data in this data set will be analyzed based on randomized treatment, except in the following cases:
 - If a subject received the same incorrect treatment throughout the 48 hours study drug infusion or until discontinuation of the study drug, then the subject will be analyzed based on the treatment received
 - If a subject received study drug from more than one treatment group, and none of the administrations were consistent with the assigned randomized treatment group, then the subject will be analyzed based on the first treatment received

- The Pharmacokinetic analysis dataset (PK Population) will consist of all subjects who receive BMS-986231 and have at least one post dose PK sample. Additionally, the Evaluable PK Population is defined as subjects who have adequate PK profiles.

7 STATISTICAL ANALYSES

SAS® version 9.2 or higher will be used for statistical analyses, tabulations and graphical presentations. S-Plus® may be also used for graphical presentations.

7.1 General Methods

Results from Part I (Cohort 1) and Part II (Cohort 2) will be presented separately, unless otherwise noted.

Except as noted otherwise, descriptive summaries will be presented for continuous variables using number of subjects (N), mean, standard deviation (SD), median, minimum and maximum. Descriptive summaries for categorical variables will utilize counts and percentages. Several analyses noted in subsequent sections will present 95% confidence intervals (CIs), but no pre-specified significance testing will be included.

Adverse events and medical history will be coded according to the most recent Medical Dictionary for Regulatory Activities (MedDRA) version. Previous and concomitant medications will be coded using the WHO Drug Dictionary.

7.2 Study Conduct

Protocol deviations identified as significant will be captured in a trial management system and reported in the CSR. Relevant protocol deviations are those that are programmable and could potentially affect the interpretability of the study results. The following protocol deviations will be defined as relevant protocol deviations and listed:

- Error in treatment assignment resulting in a subject being dosed with an incorrect treatment
- Subject not treated within 24 hours of first dose of intravenous diuretic (the time difference between start of infusion and first dose of intravenous diuretic > 24 hours)
- Systolic blood pressure (SBP) < 105 mm Hg at screening or Hour 0
- Violation of inclusion criterion 2 (b): Subjects not hospitalized for ADHF
- Violation of inclusion criterion 2 (g): Not having at least 2 of the following at time of screening:
 - i) evidence for pulmonary congestion on chest x-ray
 - ii) rales by chest auscultation,
 - iii) edema $\geq 2+$ on a 0 to 3+ scale (easily identifiable indentation, skin rebounds in 15-30 seconds)
 - iv) presence of jugular venous distention
- Violation of inclusion criterion 2 (h): Have no elevated NT-proBNP ≥ 1600 pg/mL (516 pmol/L) or BNP ≥ 400 pg/mL (116 pmol/L) as determined at the local laboratory within 18 hours prior to the start of study drug infusion. For subjects with atrial fibrillation: no NT-proBNP ≥ 2400 pg/ml or BNP ≥ 600 pg/ml

- Violation of exclusion criterion 4 (a): Subjects administered IV or transdermal nitrate therapy prior to randomization, when at least one of the following criteria are not met:
 - i) Systolic blood pressure at screening or just prior to randomization is > 120 mm Hg
AND
 - ii) The IV nitroglycerin dose is < 100 µg/min (or isosorbide dinitrate < 3 mg/hour), AND
 - iii) The infusion rate and dose has been unchanged for > 2 hours
- Violation of exclusion criterion 4 (d): Subjects treated with oral phosphodiesterase type 5 (PDE5) inhibitor sildenafil, vardenafil or avanafil within 24 hours of screening or treated with tadalafil within 4 days prior to the start of screening
- Initiation of PDE5 inhibitors during study drug infusion

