3.3.1 Inclusion Criteria

1) Signed Written Informed Consent

- a) Subjects will be required to provide a written informed consent

2) Target Population

- a) Subjects being hospitalized for ADHF
- b) Have had at least 40 mg furosemide intravenous, or equivalent (e.g 40 mg furosemide equivalent to 20 mg torsemide or to 1 mg bumetanide) for the current ADHF episode
- c) Subject must be randomized and treated within 18 hours of first dose of intravenous diuretic for Part I Cohort 1 (or 48 hours of first dose for Part II Cohort 2).
- d) Have dyspnea at rest or with minimal exertion after administration of at least 1 dose of intravenous diuretics. Subject must not be randomized within 2 hours after an IV bolus dose of intravenous diuretics, or within 2 hours after the initiation or a dose increase of an IV diuretic administered by continuous infusion
- e) Have a history of heart failure and a left ventricular ejection fraction (LVEF) $\leq 40\%$, as assessed by echocardiography, a multigated acquisition (MUGA) scan or magnetic resonance imaging (MRI) scan

Note: Ejection fraction documentation up to 18 months prior to screening may be used if there is no clinical expectation of improvement in ejection fraction in that timeframe (eg, the patient has not had biventricular pacing initiated during that period)

- f) Have at least 2 of the following at time of screening:
 - i) evidence for pulmonary congestion on chest x-ray
 - ii) rales by chest auscultation,
 - iii) edema $\geq 2+$ on a 0 to 3+ scale (easily identifiable indentation, skin rebounds in 15-30 seconds)
 - iv) presence of jugular venous distention
- g) Have an elevated NT-proBNP ≥ 1600 pg/mL (189 pmol/L) or BNP ≥ 400 pg/mL (116 pmol/L) as determined at the local laboratory within 18 hours prior to the start of study drug infusion for Part I Cohort 1 (or 48 hours for Part II Cohort 2)

For subjects with atrial fibrillation: NT-proBNP ≥ 2400 pg/ml or BNP ≥ 600 pg/ml

- h) Body weight ≥ 50 kg and < 140 kg at screening
- i) Subject Re-Screening: This study permits the re-screening of a subject that has discontinued the study as a screen failure (has not been randomized). See [Section 5.1.1](#) for more details

3) Age and Reproductive Status

- a) Males and Females, at least age 18 (or age of majority) (Germany only, see [Appendix 3](#))

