5.3.5.1 Local Laboratory Assessments for Screening

The following local laboratory tests will be assessed as part of the screening evaluation. Local Laboratory results obtained for the current episode of heart failure as part of standard of care may be used. Results will be recorded in the study eCRF.

Hematology

- Hemoglobin
- Hematocrit
- White blood cell count and differential
- Platelet count

Serum chemistry

- Aspartate Aminotransferase (AST, SGOT)
- Alanine Aminotransferase (ALT, SGPT)
- Alkaline Phosphatase
- Total Bilirubin
- Blood Urea Nitrogen (BUN)
- Electrolytes
 - Sodium
 - Potassium
- Serum Creatinine (Scr)

Other Assessments

- eGFR, by locally used equation
- Trough Serum Digoxin (if receiving digitalis glycosides)
- Hs Troponin T (or other based on site's available assays)
- Coagulation Tests
 - Prothrombin Time (PT or PT-INR)
- NT-ProBNP or BNP (as per site preference)

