3.3.1 Inclusion Criteria

1) Signed Written Informed Consent

- a) Subjects will be required to provide a written informed consent

2) Target Population

- a) Subjects being hospitalized for ADHF
- b) Have had at least 40 mg furosemide intravenous, or equivalent (e.g 40 mg furosemide equivalent to 20 mg torsemide or to 1 mg bumetanide) for the current ADHF episode
- c) Subject must be randomized and treated within 18 hours of first dose of intravenous diuretic for Part I Cohort 1 (or 48 hours of first dose for Part II Cohort 2).
- d) Have dyspnea at rest or with minimal exertion after administration of at least 1 dose of intravenous diuretics. Subject must not be randomized within 2 hours after an IV bolus

dose of intravenous diuretics, or within 2 hours after the initiation or a dose increase of an IV diuretic administered by continuous infusion

- e) Have a history of heart failure and a left ventricular ejection fraction (LVEF) $\leq 40\%$, as assessed by echocardiography, a multigated acquisition (MUGA) scan or magnetic resonance imaging (MRI) scan

Note: Ejection fraction documentation up to 18 months prior to screening may be used if there is no clinical expectation of improvement in ejection fraction in that timeframe (eg, the patient has not had biventricular pacing initiated during that period)

- f) Have at least 2 of the following at time of screening:
 - i) evidence for pulmonary congestion on chest x-ray
 - ii) rales by chest auscultation,
 - iii) edema $\geq 2+$ on a 0 to 3+ scale (easily identifiable indentation, skin rebounds in 15-30 seconds)
 - iv) presence of jugular venous distention
- g) Have an elevated NT-proBNP ≥ 1400 pg/mL (166 pmol/L) or BNP ≥ 350 pg/mL (101 pmol/L) as determined at the local laboratory within 18 hours prior to the start of study drug infusion for Part I Cohort 1 (or 48 hours for Part II Cohort 2)
For subjects with atrial fibrillation: NT-proBNP ≥ 2400 pg/ml or BNP ≥ 600 pg/ml
- h) Body weight ≥ 40 kg and < 140 kg at screening
- i) Subject Re-Screening: This study permits the re-screening of a subject that has discontinued the study as a screen failure (has not been randomized). See [Section 5.1.1](#) for more details

3) Age and Reproductive Status

- a) Males and Females, at least age 18 (or age of majority) (Germany only, see Appendix 3)

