2.4 Protocol Amendments

This statistical analysis plan (SAP) is based on the revised protocol version 01 which incorporates Amendment 01, dated 11-Oct-2016.

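### SAP 7.2 pairs the NT-proBNP limit of 1600 pg/mL with 516 pmol/L where the protocol gives 189 pmol/L, so a deviation check coded on the SI figure could list eligible subjects as violations

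*SAP*

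**What the plan says.** SAP 7.2 sets out which protocol deviations will be programmed and listed. It describes the class this way: "Relevant protocol deviations are those that are programmable and could potentially affect the interpretability of the study results". One item is failure of the natriuretic peptide entry criterion, for subjects who "Have no elevated NT-proBNP ≥ 1600 pg/mL (516 pmol/L) or BNP ≥ 400 pg/mL (116 pmol/L"). For atrial fibrillation the same item gives limits in mass units only: "For subjects with atrial fibrillation: no NT-proBNP ≥ 2400 pg/ml or BNP ≥ 600 pg/ml".

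The matching criterion in Revised Protocol 02 (section 3.3.1, item 2(g), repeated in the synopsis) reads "Have an elevated NT-proBNP ≥ 1600 pg/mL (189 pmol/L) or BNP ≥ 400 pg/mL (116 pmol/L"). Revised Protocol 02c lowers the limits: "Have an elevated NT-proBNP ≥ 1400 pg/mL (166 pmol/L) or BNP ≥ 350 pg/mL (101 pmol/L"). The summary of changes for Revised Protocol 02a, in Appendix 3 of 02c, also gives the limit being replaced as 1600 pg/mL with 189 pmol/L.

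The screening value is a local laboratory result, and the marker is "NT-ProBNP or BNP (as per site preference"), according to protocol section 5.3.5.1. SAP 2.4 states its basis: "This statistical analysis plan (SAP) is based on the revised protocol version 01 which incorporates Amendment 01, dated 11-Oct-2016".

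**The concern.** The SAP and the protocol attach different SI values to one mass concentration of one analyte, so at most one can be right. The SAP figure sits in a rule that is to be programmed, on a criterion that helps define the disease under study. The pmol/L figure matters only for results reported in pmol/L, and those are the results for which it is wrong.

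At stake is the accuracy of the deviation listing. A subject who met the entry criterion could appear as a violator because of the unit the local laboratory uses. The listing would then suggest that part of the population lacked the required peptide elevation.

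**Working it through.** This is a unit conversion that needs only the pairs printed in the documents.

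**Step 1. Implied factor, pg/mL divided by pmol/L.** The range in brackets allows for rounding of the pmol/L figure by 0.5 either way.

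| Source | Pair | Factor |
|---|---|---|
| Revised Protocol 02, NT-proBNP | 1600 / 189 | 8.466 (8.443 to 8.488) |
| Revised Protocol 02c, NT-proBNP | 1400 / 166 | 8.434 (8.408 to 8.459) |
| SAP 7.2, NT-proBNP | 1600 / 516 | 3.101 (3.098 to 3.104) |
| SAP 7.2 and Revised Protocol 02, BNP | 400 / 116 | 3.448 |
| Revised Protocol 02c, BNP | 350 / 101 | 3.465 |

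The two protocol NT-proBNP ranges overlap (8.443 to 8.459). The SAP range is far outside both.

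**Step 2. Try to reproduce 516.**
- With the factor from the separate 1400/166 pair: 1600 / 8.434 = 189.7 pmol/L. This agrees with the protocol's 189, not with 516.
- In reverse, with the 1600/189 factor: 1400 / 8.466 = 165.4 pmol/L, against the stated 166.
- With a BNP factor used by mistake: 1600 / 3.448 = 464 and 1600 / 3.465 = 462 pmol/L. A mix-up of the two markers does not give 516 either.

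The SAP figure is therefore not reproduced. The BNP pair on the same line agrees with the protocol, so the fault is confined to the NT-proBNP figure.

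**Step 3. Size of the error.**
- 516 × 8.434 = 4352 pg/mL and 516 × 8.466 = 4368 pg/mL, so 516 pmol/L is about 4350 to 4370 pg/mL.
- 516 / 189 = 2.73.

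**Step 4. Check against the atrial fibrillation limit.** 2400 pg/mL is 2400 / 8.466 = 283.5 to 2400 / 8.434 = 284.6 pmol/L. The atrial fibrillation limit is meant to be the higher of the two, yet 516 pmol/L as the general limit would exceed it.

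**Step 5. Who could be listed wrongly.** All of these must hold:
1. the program compares SI results directly with the pmol/L figure;
2. the laboratory reports NT-proBNP in pmol/L;
3. the subject does not have atrial fibrillation, because that limit has no SI figure;
4. the subject has no qualifying BNP, because either marker is enough;
5. NT-proBNP is from 189 to below 516 pmol/L, about 1600 to 4370 pg/mL.

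The documents do not say how many laboratories report pmol/L, so no count can be given.

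**The case against.** The strongest reply is that pg/mL is the stated limit and the pmol/L figure only a bracketed equivalent. The atrial fibrillation limits in the same item are given in pg/mL alone, so the whole rule cannot be run in pmol/L without a conversion. If results are converted first, the 1600 pg/mL limit works and 516 is never used. This stands: the false listing is possible, not certain. A reader might infer that every eligible subject reported in SI units will be listed as a violator. The documents do not support that, for the reasons in Step 5.

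A reader might also infer harm to the trial's results. The populations in SAP 6.3 include no per-protocol set, and under SAP 7.6 the safety analyses, including the primary one, use the Treated Subjects Data Set. Nothing in the documents removes a subject from these analyses because of this listing. Baseline NT-proBNP is summarised separately under SAP 7.3.2, so the actual elevation will be visible.

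Third, the SAP follows Revised Protocol 01, which is not available here, and its criterion lettering differs from Revised Protocol 02. The 516 may have been carried over from there. That could explain the figure but would not make it equal to the 1600 pg/mL beside it.

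Finally, it is tempting to start the affected band at 1400 pg/mL for subjects entered under Revised Protocol 02a or later. That would mix two issues. The SAP's 1600 pg/mL limit would flag subjects between 1400 and 1600 pg/mL in either unit, and would still do so with 189 in place. That is a question of which protocol version the SAP should follow.

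**Conclusion.** The point holds as an error in the SAP text with a conditional consequence. On the documents' own conversions, 516 pmol/L is wrong for 1600 pg/mL and 189 pmol/L is right. This does not depend on which protocol version the SAP follows. The SI limit is overstated 2.73-fold.

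The consequence rests on the assumption that the check is coded on the pmol/L figure for at least some results. In that case the listing would depend on the laboratory's unit within the band in Step 5. The number of subjects is unknown and could be zero. The effect stops at the listing of relevant deviations. It is still worth correcting, because the SAP specifies the program and now gives two incompatible limits for one entry criterion.

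**What to change.** In SAP 7.2, replace 516 pmol/L with 189 pmol/L beside 1600 pg/mL. State that the check will be run on results converted to pg/mL, and give the conversion factor. A factor of 1600/189 = 8.466 keeps the two printed limits equivalent. With 8.434, a result of exactly 189 pmol/L would convert to 189 × 8.434 = 1594 pg/mL and be flagged at the boundary.

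Whether the SAP should adopt the later limit of 1400 pg/mL (166 pmol/L) is a separate matter of version alignment. If it is adopted, both units must change together; putting 166 pmol/L beside an unchanged 1600 pg/mL would create a new mismatch.

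The cost is one number in the SAP and one conversion in the deviation program. No entry rule, treatment or analysis changes.

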7.3 Study Population

7.3.1 Subject Disposition

Subject disposition will be listed. Summary tables reflecting the number of subjects who are enrolled, who are randomized, and reasons for not being randomized, will be presented as overall.

The number of subjects who do not complete the treatment of 48 hours infusion, both overall and according to reasons for discontinuation from the treatment, will be summarized for all treated subjects, as overall and by treatment. Subjects who have temporary interruption or down-titration of study drug but do not discontinue permanently will be treated as completing the treatment. The number of subjects who do not complete the study phase, both overall and according to reasons for not completing, will be summarized for all treated subjects, as overall and by treatment. Summary tables will be presented for study phases ending at Hour 120 (or discharge, whichever comes first), Day 32, and Day 182.

